1.0 STUDY OBJECTIVES AND HYPOTHESES

1.1 Study Primary Objective:

CCTG 595 will compare adherence to fixed dose TDF/FTC, between subjects randomized to receive SoC plus text message reminders versus SoC, when used for pre-exposure prophylaxis among MSM at high risk for HIV acquisition.

1.1.1

Hypothesis I

MSM and transgender M to F having sex with men with high risk of HIV acquisition randomized to the iTAB intervention will have higher self-reported adherence to TDF/FTC for PrEP over 48 weeks ('adherent' defined with a composite endpoint of continued retention on PrEP and \geq 90% adherence to TDF/FTC at 48 weeks) compared to MSM that have comprehensive SoC alone.

1.1.2

Hypothesis II

MSM and transgender M to F having sex with men with high risk of HIV acquisition randomized to the iTAB intervention will have higher adherence to TDF/FTC for PrEP over 48 weeks, as measured by having five of five detectable qualitative FTC plasma concentrations at scheduled visits compared to MSM that have comprehensive standard of care alone.

1.2 Study Secondary Objectives:

1.2.1

To compare adherence to TDF/FTC in the iTAB versus SoC in the subjects that remain on PrEP (at 48 weeks and up to 96 weeks of follow up) by the continuous measure of percent days adherent by the cumulative 4 day ACTG and the visual analog scale (VAS) recall in an 'as treated' analysis.

1.2.2

To compare adherence to TDF/FTC in the iTAB versus SoC groups for the duration of the study (up to 96 weeks). Adherence will be compared using the same outcomes as hypothesis I (self-reported to be on drug and 90% adherent) and II (100% detectable FTC at each scheduled visit) as modified intent to treat analysis.

1.2.3

To determine factors associated with poor adherence/lost to PrEP in study participants (outcomes of < 90% adherent on drug at 48 weeks by ACTG 4 day recall or discontinuation of drug). Factors associated with poor adherence to TDF/FTC will include demographics, ongoing

substance use, untreated mental illness, socioeconomic status, low health/HIV and system literacy, fear of disclosure and non-English language.

- 1.2.4 To determine the factors associated with discontinuation of TDF/FTC at any time point including change in perceived and actual risk of HIV acquisition, demographics, ongoing substance use, untreated mental illness, socioeconomic status, low health/HIV and system literacy, fear of disclosure and non-English language.

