9.2 Secondary Endpoints

- 9.2.1 Adherent to PrEP by FTC measurement at 48 weeks and at the end of study follow-up is defined by attending all scheduled visits and having detectable FTC.
- 9.2.2 Adherent to PrEP in continuous follow up is aggregate percentage of self-reported ACTG days of adherence where missed schedule visits are counted as 0/4 days.
- 9.2.3 Poor adherence is considered those with <90% self-reported adherence by ACTG 4 day survey or if discontinued drug. Subgroup analysis should explore the endpoint for discontinuation for reasons other than quit drug for lack of risk or confirmed adverse event.
- 9.2.4 Safety and tolerability defined as: i) discontinuation of TDF/ FTC for any

toxicity; ii) grade 2 or higher adverse event or laboratory toxicity; iii) serious adverse event; iv) death

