9.4 Study Power and Sample Size Justification

The primary objective for this study is to compare the proportion of subjects that reach the composite endpoint, defined as: continued retention and adherence to PrEP. Sample size calculations were based on a two-sided, two- sample binomial test to compare the differences in composite endpoint proportions between the intervention arm and the standard of care arm. Since attrition is a component of the composite endpoint, attrition rates are not used as an adjustment in the power calculations. Assuming 200 subjects per group in each of the two groups (for a total of 400 subjects) and alpha set to 0.05, we have 94% power to detect a difference of 15%, assuming that 30% with a composite endpoint rate in standard of care and that 15% with endpoint in the intervention arm. We have 84% power to detect as small a difference of 13% between the two groups (i.e., 30% versus 17%).

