The primary adherence endpoint will be a binary endpoint (Yes/No) based on DBS samples from two visits (week 12 visit and the last on-drug visit over the 48 weeks). Both visits should have a detectable TFV-DP level >719 fmol/punch (consistent with taking four or more doses per week) to be considered adherent. If the last on-drug visit was at week 12 (i.e. the subject had only one DBS sample), adherence will only be determined by that sample. If a subject discontinued study before week 12 (i.e. had no DBS samples at all), the subject will be considered non-adherent.

Additional Secondary Adherence Endpoints

- Self-reported Adherence: a binary composite endpoint of continued on PrEP and $\geq 90\%$ self-reported adherence to TDF/FTC over 48 weeks. The endpoint will be defined yes if 14 or 15 out of 15 days were reported 'adherent' on the 3-day recall on the clinical assessment form collected at w4, w12, w24, w36, and w48. Note if a subject discontinued the study or missed any visits before w48, those visits will be considered not adherent in the calculation.
- a continuous version of the self-reported adherence measure: defined as percent days that were reported adherent based on the clinical assessment form. In the case where the adherence measure is missing (either due to the subject discontinued PrEP, or missed visit, or other reasons), two approaches will be applied.
 - treat the missing as 'not adherent'. This assumes the worst case (i.e. assume all the missing is related to adherence).
 - ignore the missing. This assumes the best case (i.e. assume all the missing is not related to adherence).
- FTC Adherence: a binary endpoint of having four of four detectable qualitative FTC plasma concentrations (measured at w12, w24, w36, and w48) over 48 weeks. Detectable FTC is defined as a quantitative level of ≥ 0.35 ug/ml consistent with taking a dose in past 24 hours. Note missing will be treated as not detectable.
- Similar outcome as the primary endpoint where we will use the cut-off of ≥ 1246 fmol/punch consistent with taking seven doses per week.
- Proportion of subjects on PrEP at week 48.

Descriptive Analysis

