Descriptive analysis will look at self-reported adherence, FTC adherence and TFV-DP adherence measures by visit. Continuous outcome will be summarized with N, min, Q1, median, Q3, and max, by study arm and overall. Binary endpoint will be summarized with frequency tables, by study arm and overall. Wilcoxon rank sum test will be used for comparison for continuous outcome; Fisher's exact test will be used for binary outcome.

Statistical Inference

A logistic regression model will be performed to compare the adherence over 48 weeks between the two groups. The model will include baseline factors (refer to the baseline variable list) as covariates if they are found unbalanced between the study arms (with $p < 0.1$) and also univariately associated with the outcome ($p < 0.15$). Interactions between each of the covariates and study arm will also be assessed individually. Significant interactions ($p < 0.05$) will be included in the final model.

7 Evaluation of Secondary Objectives

7.1 Secondary Objective 1

To determine factors associated with poor adherence/lost to PrEP in study participants. Factors will include demographics, ongoing substance use, untreated mental illness, socioeconomic status, low health/HIV and system literacy, fear of disclosure and non-English language.

This objective will be assessed along with the primary objective analysis. The final primary multivariable model will be able to answer this question.

7.2 Secondary Objective 2

To determine the rate of HIV seroconversion in PrEP users and compare the iTAB to SoC arms for number of new infections as a proportion at 48 weeks and end of the study.

Number and proportion of subjects with HIV-seroconversion at 48 weeks will be summarized by study arm and overall. Fisher's exact test will be used for comparison. Same analysis will also look at the rate of seroconversion during the whole study period.

7.3 Secondary Objective 3

To measure acquisition of other sexually transmitted infections (STIs); the proportion of subjects with any new STI at any site will be compared between the iTAB to SoC arms at 48 weeks and end of the study.

Any new STI will be defined as positive results from Gonorrhea (GC) or Chlamydia (CT) at any site or positive syphilis RPR result with titer $>1:4$ based on the STI form collected after baseline visit.

Sensitivity analysis will also be performed looking at STI by testing as well as self-reported STI (outside diagnosis) based on the clinical assessment form.

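### SAP 7.1 uses the primary model to study loss to PrEP, but the SAP primary endpoint counts stops after week 12 with adequate drug levels as adherent

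*SAP*

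**What the plan says.** **Primary endpoint (SAP section 6).** The binary endpoint is "based on DBS samples from two visits (week 12 visit and the last on-drug visit over the 48 weeks", and both samples must exceed 719 fmol/punch. For a participant whose last on-drug visit was week 12, the text is "the subject had only one DBS sample), adherence will only be determined by that sample". For one who left before week 12 it is "had no DBS samples at all), the subject will be considered non-adherent". The model is then described as follows: "A logistic regression model will be performed to compare the adherence over 48 weeks between the two groups".

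**Factors objective (SAP 7.1).** The objective covers factors for both poor adherence and loss to PrEP. The method is one sentence: "The final primary multivariable model will be able to answer this question".

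**Protocol outcome for the same objective.** Protocol 1.2.3 gives "outcomes of < 90% adherent on drug at 48 weeks by ACTG 4 day recall or discontinuation of drug". Protocol 9.2.3 agrees: "Poor adherence is considered those with <90% self-reported adherence by ACTG 4 day survey or if discontinued drug".

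**Samples and stopping (protocol 6.3.12, 6.4 and 6.3.5).** DBS storage starts at week 12. Participants who stop drug may stay on study, but they cannot restart and DBS are no longer collected. Stops are recorded on a dedicated discontinuation CRF.

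**Power (protocol 9.4).** With 200 per arm the protocol gives 94% power for 30% versus 15% and 84% for 30% versus 17%. It adds: "Since attrition is a component of the composite endpoint, attrition rates are not used as an adjustment in the power calculations". The SAP has no power section.

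**The concern.** The outcome that SAP 7.1 borrows does not contain the event that SAP 7.1 is meant to explain. A participant who stops at week 13, 25 or 37 after passing samples is lost to PrEP under the protocol's definition but adherent in the model. Early loss is captured, and so is a late stop preceded by a low last on-drug sample. Late loss after good samples is not. A baseline factor that leads people to stop PrEP later in the year could then look unrelated to the outcome, because those people sit in the comparison group.

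A smaller matter follows from the same rule. The protocol made no attrition adjustment because attrition counted as failure. Under the SAP endpoint that is no longer so for these late stops, so the protocol's power figures cannot be read as the power of the SAP's primary comparison.

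**Working it through.** **1. The protocol's power figures.** Inputs from protocol 9.4: n = 200 per arm, two-sided alpha 0.05, 30% versus 15% and 30% versus 17%. The lower rate is in the intervention arm, so these read as failure rates; 70% versus 85% gives the same power. With a continuity correction,

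power = Φ{[|p1 − p2| − 1/n − 1.96·√(2p̄(1 − p̄)/n)] / √[(p1(1 − p1) + p2(1 − p2))/n]}

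- 30% v 15%: (0.145 − 0.0818)/0.0411 = 1.54, power 93.8%.
- 30% v 17%: (0.125 − 0.0831)/0.0419 = 1.00, power 84.1%.

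Exact power of Fisher's test, the protocol's planned test, is 94.0% and 84.5%. Both stated figures reproduce.

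**2. How many lost participants are coded adherent.** The documents give none of these rates, so all are assumptions:

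- e = share stopping before week 12, set at 5%
- s = share stopping between week 12 and week 48, 10% to 25%
- q = probability of passing the >719 rule, 85%
- q_stop = the same probability among late stoppers, equal to q or 50%
- N = 400, all in the modified intent-to-treat population. DBS failure stands in for poor adherence.

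Poor or lost = N × [e + s + (1 − e − s)(1 − q)]. Of these, coded adherent by the primary endpoint = N × s × q_stop.

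| s | Poor or lost | Coded adherent, q_stop = 85% | Coded adherent, q_stop = 50% |
|---|---|---|---|
| 10% | 400 × (0.05 + 0.10 + 0.85 × 0.15) = 111 | 34 (31%) | 20 (18%) |
| 25% | 400 × (0.05 + 0.25 + 0.70 × 0.15) = 162 | 85 (52%) | 50 (31%) |

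With q_stop = q and q varied from 70% to 95%, the share runs from 28 of 162 (17%; s = 10%, q = 70%) to 95 of 134 (71%; s = 25%, q = 95%). Varying e from 0% to 10% at q = 85% gives 34 of 94 to 34 of 128 (36% to 27%) for s = 10%, and 85 of 145 to 85 of 179 (59% to 47%) for s = 25%.

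**3. What this does to a factor for stopping.** Compare two groups that differ only in late stopping, 10% versus 25%, with e = 5% and q = 85%.

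- SAP endpoint, stoppers passing like others: 0.95 × 0.85 = 80.75% adherent in both groups. s drops out, so the difference is 0.
- SAP endpoint, stoppers passing 50% of the time: 0.85 × 0.85 + 0.10 × 0.50 = 77.25% versus 0.70 × 0.85 + 0.25 × 0.50 = 72.0%, a difference of 5.25 points.
- Outcome that counts stopping as failure: 0.85 × 0.85 = 72.25% versus 0.70 × 0.85 = 59.5%, a difference of 12.75 points.

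**4. Whether the power figures carry over.** Start from 30% v 15% failure and move late stoppers with adequate levels from failure to adherent (assumed amounts, exact Fisher):

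- 10 points in each arm: 20% v 5%, power 99.6%.
- One fifth of the failures in each arm: 24% v 12%, power 85.7%.
- 15 points in SoC and 5 in iTAB: 15% v 10%, power 27.6%.

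Power can rise or fall.

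**The case against.** Much can be said for the SAP as it stands. Protocol 9.0 gives the SAP precedence over the protocol's statistical section, so replacing the self-report composite with a DBS endpoint is allowed. The rule is explicit, including the one-sample and no-sample cases. Protocol 1.2.1 already recognises adherence among those still on PrEP as a legitimate question. Retention has not vanished either: the SAP reports the proportion on PrEP at week 48, a self-report composite that requires continued PrEP, four-of-four detectable FTC with missing counted as undetectable, and study exit by arm. All of that stands.

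A reader might infer three stronger things, and the documents support none of them.

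- *That the 94% and 84% are wrong.* They reproduce and are correctly attached to the protocol's composite. The SAP does not repeat them for its own endpoint.
- *That the trial has lost power.* The direction depends on rates the documents do not give.
- *That the DBS rule is the wrong primary endpoint.* Neither rule is better in all cases. With 25% late stops in both arms and passing rates of 85% v 95%, the SAP rule gives 80.75% v 90.25% (power 77%), while a composite gives 59.5% v 66.5% (power 30%).

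It can also be argued that where the SAP is silent the protocol stands, including time to discontinuation for any reason (9.6.5) and the logistic models of factors for the on-therapy composite (9.6.4). The first compares arms and does not model factors. The second is displaced because SAP 7.1 is not silent: it repeats the objective and names a different model. Protocol 1.2.4, on factors for discontinuation, is not among the SAP's objectives. So this reply does not rescue SAP 7.1.

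Finally, the sizes above are assumed. That is true, and they are offered only as illustrations.

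**Conclusion.** SAP 7.1 is wrong as written. The primary model places PrEP stops after week 12 with adequate samples in the adherent group, so it cannot answer the lost-to-PrEP half of the objective. This follows from the text and needs no assumed rate.

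The size does depend on assumptions. At a 5% early stop rate, 10% to 25% late stops and an 85% pass rate, 31% to 52% of poor or lost cases are coded adherent; if stoppers pass half the time, 18% to 31%. The share is small only if late stops are rare or are mostly preceded by a failing sample.

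The power point is narrower: the protocol's figures are right for the protocol's endpoint and do not apply to the SAP's. Whether the primary target is adherence while on drug or adherence with persistence to week 48 is for the team to choose; stating it would help interpretation, but its absence is not an error. The point should be fixed, and it concerns a secondary objective rather than the validity of the primary comparison.

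**What to change.** - **SAP 7.1.** Replace reuse of the primary model with a separate logistic model. Its outcome should code PrEP discontinuation before week 48 (from the discontinuation CRF) or study exit as poor adherence/lost to PrEP, alongside failure on a named adherence measure.
- **Covariates.** Enter the factors that SAP 7.1 lists whether or not they differ between arms. The primary model admits a baseline factor only if it is unbalanced (p < 0.1) and associated with the outcome (p < 0.15), so it would omit a balanced predictor whatever the outcome. Untreated mental illness and fear of disclosure are not on the SAP section 5 baseline list and need named variables.
- **Reasons for stopping.** Add the analysis that protocol 9.2.3 asks for, separating stops for lack of risk or a confirmed adverse event from other stops.
- **Power.** State that 94% and 84% refer to the protocol's self-report composite and do not apply to the DBS endpoint, because attrition after week 12 is no longer failure by rule and the direction of change is unknown.
- **Optional.** State the primary target, and report a DBS composite that counts stops before week 48 as non-adherent as a supplementary analysis.

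The cost is SAP text, one derived variable, one extra model and a little more analysis work. No new samples or participants are needed.

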Clinical Trials Specialist

[name]
Staff Research Associate
University of California, San Diego
Antiviral Research Center
[name]
San Diego, CA 92103
[contact]
[contact]
E-mail [contact]

Statistician

[name]
Associate Professor, Division of Biostatistics and Bioinformatics
Director, CCTG Biostatistics Core
Co-Director, Biostatistics Research Center (BRC)
University of California, San Diego
[name]
La Jolla, CA 92093-0717
[contact]
E-mail [contact]

Study Monitor and Data Unit

[name]
Medical Monitor, Study Coordinator, CCTG Data Unit
University of California, San Diego
Antiviral Research Center
[name]
San Diego, CA 92103
[contact]
[contact]
E-mail [contact]

Lab Technician

[name]
Phlebotomist and Lab Manager
University of California, San Diego
Antiviral Research Center

[name]
San Diego, CA 92103
[contact]
[contact]
E-mail [contact]

LIST OF ABBREVIATIONS

AE	Adverse Event
ALERT	Active Linkage, Engagement, and Retention to Treatment
ARV	Antiretroviral Therapy
CCTG	California Collaborative Treatment Group
CD4	CD4 Lymphocytes
CRF	Case Report Form
CT	Chlamydia
DSMB	Data Safety and Monitoring Board
GC	Gonorrhea
HAART	Highly Active Antiretroviral Therapy
HIV-1	Human Immunodeficiency Virus – 1
iTAB	Individualized Texting for Adherence Building
mITT	Modified Intention to Treat
MSM	Men who have Sex with Men
NAAT	Nucleic Acid Amplification Test
PLWH	Persons Living With HIV/AIDS
PrEP	Pre-Exposure Prophylaxis
RPR	Rapid Plasmin Reagin
SAP	Statistical Analysis Plan
SAE	Serious Adverse Event
SoC	Standard of Care
STI	Sexually Transmitted Infection
TPPA	Treponema Pallidum Particle Agglutination Assay
VAS	Visual Analog Scale
VDRL	Venereal Disease Research Laboratory

[figure not shown]
SCHEMA

Design: CCTG 595 is a controlled, open-label, two-arm, randomized (1:1) clinical demonstration project to determine if the use of a text-message based adherence intervention (iTAB) improves retention and adherence to PrEP compared to standard of care (SoC) PrEP delivery.

Duration: Each subject will be followed for up to 48 weeks after enrollment of the last subject to a maximum of 96 weeks. The primary endpoint will be measured at 48 weeks.

Sample Size: A total of 400 subjects will be randomized, 200 per arm.

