9.0 STATISTICAL CONSIDERATIONS

A formal Statistical Analysis Plan (SAP) will be drafted and finalized prior to database lock. The SAP will contain a more detailed and/or comprehensive presentation of statistical methods, attention to any changes of substance to planned analysis procedures relative to those indicated in the protocol, and is the final authority for all statistical analyses. The following section briefly describes the planned statistical analyses. In case the language in this section differs from the language in the SAP, the SAP takes precedence.

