9.1 Primary Endpoints

Adherent to PrEP through 48 weeks is defined as a composite endpoint of continuing on study (made all scheduled visits within window in the 48 week period) and on study medication and greater than or equal to 90% adherent to medication defined by self-report of ≥ 18 of 20 doses of medication on the 5 ACTG adherence questionnaires at weeks 4, 12, 24, 36 and 48. Missing adherence forms will be imputed as no doses taken.

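### The SAP replaces the protocol's primary endpoint without acknowledging it, and its planned outputs cannot reproduce the protocol's primary result

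*SAP*

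**What the plan says.** The protocol's primary endpoint (Schema, and section 9.1) is a composite. It requires "continuing on study (made all scheduled visits within window in the 48 week period", being on study medication, and "self-report of ≥ 18 of 20 doses of medication on the 5 ACTG adherence questionnaires at weeks 4, 12, 24, 36 and 48". On gaps it says: "Missing adherence forms will be imputed as no doses taken". Section 9.6.2 plans Fisher's exact test with a 95% confidence interval.

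SAP section 6 has a different primary endpoint: "The primary adherence endpoint will be a binary endpoint (Yes/No) based on DBS samples from two visits". These are week 12 and the last on-drug visit within 48 weeks. TFV-DP must exceed 719 fmol/punch at both, a level that the SAP equates with four or more doses a week. If week 12 was the last on-drug visit, that single sample decides.

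Among the secondary endpoints, the SAP keeps a self-report composite: continued on PrEP with at least 90% adherence, at weeks 4, 12, 24, 36 and 48, with missed visits counted as not adherent. It is scored from a 3-day recall on the clinical assessment form: "The endpoint will be defined yes if 14 or 15 out of 15 days were reported".

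Protocol section 9.0 gives the SAP precedence. It also says that the SAP will contain "attention to any changes of substance to planned analysis procedures relative to those indicated in the protocol".

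**The concern.** A change of primary endpoint is the change that a reader most needs to see, with its date and its reason. The SAP presents the TFV-DP endpoint as if it had always been primary. Its section 3.1 restates the hypothesis without the word self-reported and without the composite definition that protocol section 1.1.1 attaches to it.

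The trial is described as follows: "CCTG 595 is a controlled, open-label, two-arm, randomized (1:1) clinical demonstration project". In an open-label trial, staff may learn how the arms compare while data accrue, so a dated statement matters more than it would under blinding.

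The replacement also differs in substance. The protocol endpoint cannot be met without staying on PrEP to week 48; the SAP endpoint can. And because the self-report composite is rescored, nothing in the planned outputs shows what the protocol's own primary analysis would have found. A reader who wants to know whether the conclusion depends on the switch cannot find out.

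**Working it through.** **1. The plan's own figure.** Protocol section 9.4 gives power for its composite with 200 per arm and two-sided alpha 0.05: 94% for 30% v 15%, and 84% for 30% v 17%. With a continuity correction, z = (|p1 − p2| − 1/n − 1.96·SE0)/SE1.

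- 30% v 15%: SE0 = √(2·0.225·0.775/200) = 0.0418 and SE1 = √((0.3·0.7 + 0.15·0.85)/200) = 0.0411. Then z = (0.150 − 0.005 − 0.0818)/0.0411 = 1.54, so power is 93.8%.
- 30% v 17%: the same steps give z = 1.00, so power is 84.1%.

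Exact enumeration of Fisher's test gives 94.0% and 84.5%, so both stated figures reproduce. (The direction fits the hypothesis only if these are failure rates; power is the same for 70% v 85% adherent.) They belong to the protocol composite. The documents give no expected rates for TFV-DP.

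**2. The three definitions side by side.**

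| | Protocol primary (9.1) | SAP primary (6) | SAP self-report secondary (6) |
|---|---|---|---|
| Source | ACTG 4-day questionnaire | Dried blood spot TFV-DP | 3-day recall, clinical assessment form |
| Visits | 4, 12, 24, 36, 48 | 12 and last on-drug | 4, 12, 24, 36, 48 |
| Cut-off | ≥18/20 | >719 fmol/punch | ≥14/15 |
| On PrEP to week 48 needed | Yes | No | Yes |

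Protocol section 6.3.12 stores dried blood spots only for possible future use. The ACTG review is scheduled at every follow-up visit (sections 6.1 and 6.2.3), so the data for the protocol endpoint are collected.

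**3. A subject who stops PrEP after the week 12 visit.**

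- Protocol endpoint: at most 2 × 4 = 8 of 20 days (40%), and not on medication. Fails.
- SAP self-report endpoint: at most 2 × 3 = 6 of 15 days (40%). Fails.
- SAP primary: the week 12 sample alone decides. Adherent if above 719.

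The required dosing differs too: four doses a week is 4/7 = 57%, against 90% in the protocol.

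**4. The two self-report rules.** 18/20 = 90.0% tolerates two missed days. 14/15 = 93.3% tolerates one, since 13/15 = 86.7% falls below 90%. One missed visit fails under both (16/20 and 12/15, each 80%).

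For subjects who attend every visit, assume independent days with daily probability p of taking the dose. The documents give no p, so a range is shown. P(≥18/20) = 190p¹⁸(1−p)² + 20p¹⁹(1−p) + p²⁰, and P(≥14/15) = 15p¹⁴(1−p) + p¹⁵.

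| p | ≥18/20 | ≥14/15 | Gap (points) |
|---|---|---|---|
| 0.80 | 20.6% | 16.7% | 3.9 |
| 0.85 | 40.5% | 31.9% | 8.6 |
| 0.90 | 67.7% | 54.9% | 12.8 |
| 0.95 | 92.5% | 82.9% | 9.5 |
| 0.98 | 99.3% | 96.5% | 2.8 |

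Nor is either rule contained in the other, even if both forms record the same days. Two misses inside the 3-day windows give 18/20 (pass) and 13/15 (fail). Three misses that all fall on the fourth day back give 17/20 (fail) and 15/15 (pass). One result cannot be derived from the other.

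**5. Disclosure and timing.** No section of the SAP covers changes from the protocol. The SAP is dated March 18, 2016. The vitamin D sub-study (section 2.1) puts enrolment at about one third of 400 by April 2014, so subjects then enrolled and still followed would have reached week 48 by about March 2015. Self-report surveys are stored automatically in the database (protocol section 11.1). Data for the protocol endpoint therefore very probably existed when the SAP was dated. The documents do not say whether anyone had seen them by arm.

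**The case against.** The strongest defence is that the SAP was entitled to do this. Protocol section 9.0 makes it the final authority. Hypothesis II (section 1.1.2), also under the primary objective, is already a drug-level measure. Section 3.1 says that self-report and FTC levels both feed the main and secondary analyses, and section 10.1 foresees further pharmacology analyses specified in the SAP before samples are tested. A laboratory measure is also less exposed to open-label reporting bias than self-report. All of this stands. It makes the change permissible and arguably an improvement, but it does not disclose it.

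The defence also rightly limits three inferences that a reader might draw:

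- *That the self-report composite has been dropped.* It has not. The same construct, visits and missed-visit consequence survive as a secondary endpoint; what is missing is the ACTG 18-of-20 scoring and the in-window visit requirement.
- *That Hypothesis I is never tested.* Section 1.1.1 names neither the ACTG form nor 18 of 20, and the SAP's secondary composite addresses it.
- *That retention on PrEP is ignored.* Only the TFV-DP endpoint omits it. The SAP also lists the proportion on PrEP at week 48 and compares premature study discontinuation between arms (section 4.2).

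**Conclusion.** The point holds in this form: the primary endpoint changed in substance, the SAP does not say so despite the commitment in protocol section 9.0, and the protocol endpoint as defined is not among the planned analyses. The retained self-report rule is not a substitute. Its classification rate is lower by up to about 13 percentage points over the range shown, assuming independent days and full attendance. That gap is in the share classed adherent, not in the difference between arms, and the documents give no basis for estimating the effect on the treatment comparison.

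A reader might infer from the open-label design and the SAP's date that the endpoint was switched after seeing results. The documents do not support that: they are silent on who had seen adherence data by arm, protocol section 6.3.11 has stored specimens shipped in batches after study completion, and section 10.1 has FTC assayed at the end of follow-up. What is established is a missing statement and a missing analysis, both worth correcting.

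**What to change.** Add to SAP section 6, as a named secondary analysis in the mITT population, the endpoint exactly as protocol section 9.1 defines it: all five visits made in window, on study medication, at least 18 of 20 ACTG days, and a missing form scored 0 of 4. Analyse it with Fisher's exact test and a 95% confidence interval, as protocol section 9.6.2 already planned. Beside it, add a short paragraph giving the date of the change of primary endpoint, the reason for it, and whether adherence data by arm had been seen.

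The cost is one 2×2 table on data already collected and one paragraph. The downside is one more secondary result, which partly overlaps the 14-of-15 endpoint.
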